5) Stratified analysis: According to the center, stratified analysis is carried out on the 28-day mortality rate, and mNGS-guided treatment are explored for related effects on the prognosis of patients with severe community-acquired pneumonia.

(3) Statistical analysis content

Statistical analysis content

1). General principles of statistical analysis

All statistical tests use two-sided tests. After P value is adjusted by FDT, Q value ≤ 0.05 will be considered as statistically significant (unless otherwise specified). The description of quantitative indicators will calculate the mean, standard deviation, median, minimum, maximum, lower quartile(Q1), upper quartile (Q3), and classification indicators to describe the number of cases and percentages of each category. The general comparison of the two groups will be analyzed by appropriate methods according to the types of indicators. The comparison of quantitative data between groups will be based on the data distribution using group t test (homogeneity of variance, normal distribution) or Wilcoxon rank sum test, The classification data uses the chi-square test or the exact probability method (if the chi-square test is not applicable), and the rank data uses the Wilcoxon rank sum test or the CMH test. Kaplan-Meier description, Log-rank test and Cox regression were used for the survival time data of the study subjects. The research results of each research center are evaluated by meta-analysis to evaluate the heterogeneity and the overall research merger effect. The potential confounding bias (treatment, service, management, etc.) of each research center is analyzed using a multi-layered mixed model.

2). Baseline and demographic characteristics

Summarize the number of enrollment and make a list of dropped cases. The size of the data set in each group, the distribution of cases in each center, the comparison of the total dropout rate, and a detailed list of the reasons for termination.

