The demographic characteristics (age, sex, height, body mass index, vital signs, etc.), history of allergies, etc. of the subjects were statistically described. According to the numerical characteristics of the variables, the t-test/Wilcoxon rank sum test was used to compare the quantitative data of the two groups of subjects such as age, height, and body mass index; the chis-square test/exact probability method was used to determine the gender of the subjects, post medical history, allergy history and other categorical variables for comparison.

Analysis of dropped cases: Cases that meet the criteria for dropped cases and the subjects withdrew from the study should be included in the dropped case analysis. The total dropout rate between groups and the dropout due to adverse events were compared using the chi-square test.

3). Effectiveness analysis

(1) Baseline index: Describe the baseline of each curative effect index, refer to general statistical methods for the comparison method between groups. A stratified analysis was performed based on the

center.

(2) Main efficacy indicators: The relative change in SOFA score from randomization to day 5, day 7, day 10, or the day of ICU discharge/death; and the consumption of antimicrobial agents during ICU stay (expressed as defined daily doses). Simultaneous FAS analysis and PPS analysis.

(3) Secondary curative effect index

- ①days from randomization to initiation of definitive antimicrobial treatment
- ②overall antimicrobial agent use and cost;
- ③total cost of hospitalization;
- ④length of ICU stay;
- ⑤28- and 90-day mortality; and clinical cure rate.

For all the outcome indicators, first conduct independent evaluation in each research center in accordance with general principles. Then meta-analyze the research results of each research center. Assess the heterogeneity and the combined effect of the overall study. Finally, a multivariate stratified mixed model was used to adjust the potential bias.

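### Apart from being the endpoint's reference value, baseline SOFA is committed to no analysis of the SOFA effect, and no analysis step is named primary (optional, low-cost improvement)

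*Combined protocol and SAP*

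**What the plan says.** All references are to the Combined protocol and SAP.

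- **Endpoint.** Section 3) Effectiveness analysis, item (2) Main efficacy indicators, lists "The relative change in SOFA score from randomization to day 5, day 7, day 10, or the day of ICU discharge/death". No formula is given. I read it as change divided by the value at randomisation.
- **Baseline.** Item (1) Baseline index of the same section says: "Describe the baseline of each curative effect index, refer to general statistical methods for the comparison method between groups". SOFA is covered as one of those indices. The only stratification attached to this item is by centre.
- **Effect analysis.** For every outcome, the end of section 3) sets three steps. The first is "first conduct independent evaluation in each research center in accordance with general principles". For quantitative data, section 1) General principles makes that a comparison "using group t test (homogeneity of variance, normal distribution) or Wilcoxon rank sum test", neither of which carries a covariate. The centre results are then combined by meta-analysis. The last step reads: "Finally, a multivariate stratified mixed model was used to adjust the potential bias".
- **Content of the mixed model.** The only description is in section 1): "The potential confounding bias (treatment, service, management, etc.) of each research center is analyzed using a multi-layered mixed model". There is no covariate list.
- **Priority.** The three steps have an order of work. None is called primary or confirmatory.

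**The concern.** Dividing by the baseline score does not, in general, make the result independent of it. A patient who starts at a low score can show a large relative change from a shift of one or two points. If relative change still depends on baseline SOFA, leaving that score out of the model leaves explainable variation in the residual, and a chance difference in baseline between the arms moves the estimated effect.

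The plan also compares baseline SOFA between arms and leaves the mixed model's covariates open. The decision to adjust could therefore be taken after the imbalance, or the result, has been seen. With no primary step named, the unadjusted centre tests, the pooled estimate and the mixed model may disagree with no rule for which one counts. SOFA change is one of only two main indicators, so this bears on the trial's headline result.

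**Working it through.** The plan states no sample size, power, SD, effect, correlation or number of centres, so there is no figure of its own to reproduce. Every input below is an assumption.

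**1. When relative change depends on baseline.** Let B be baseline SOFA, F follow-up SOFA and R = (F − B)/B = F/B − 1.
- Proportional case: F = B × K with K independent of B gives R = K − 1. Baseline has nothing to add.
- Linear case: E(F | B) = a + bB gives E(R | B) = a/B + b − 1. R depends on B unless a = 0.

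**2. Inputs.** Baseline SOFA mean 8, SD 3.2; follow-up mean 6.5 or 8, SD 4; effect 1.2 points; correlation ρ = 0.3, 0.5 or 0.7. At face value, before rounding, bounding and centre effects, b = ρ × 4/3.2 = 1.25ρ and a = (follow-up mean) − 8b. For ρ = 0.3, for example, b = 0.375, 8b = 3, and a = 6.5 − 3 = 3.5 or 8 − 3 = 5.

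**3. Simulation.** Ten centres of 15 + 15 (150 per arm), centre SD 0.8 on baseline and on follow-up, scores rounded and held to 0–24 with baseline at least 2, two-sided 0.05 before the plan's multiplicity step. There were 10,000 replicates for power and 16,000 under no effect. Both models of R contain arm and centre; the question is what adding baseline SOFA does. The linear model stands for the planned mixed model, with centre effects fixed.

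| Follow-up mean | ρ | a | Linear model: power without/with baseline | Gain (points) | N ratio | Rank model: gain (points) | No effect, baseline means >0.6 apart: linear model rejects without baseline |
|---|---|---|---|---|---|---|---|
| 6.5 | 0.3 | 3.5 | 58/63% | +5.3 | 0.88 | +2.7 | 10.9% |
| 6.5 | 0.5 | 1.5 | 74/75% | +0.9 | 0.98 | +0.1 | 7.2% |
| 6.5 | 0.7 | −0.5 | 90/90% | +0.2 | 0.99 | +0.4 | 5.9% |
| 8 | 0.3 | 5.0 | 53/61% | +8.9 | 0.81 | +6.5 | 14.1% |
| 8 | 0.5 | 3.0 | 69/72% | +3.7 | 0.92 | +1.5 | 8.7% |
| 8 | 0.7 | 1.0 | 89/89% | +0.2 | 0.99 | −0.1 | 5.8% |

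The gain in the linear model follows the size of a, as step 1 predicts, and is about nil at ρ = 0.7 for both follow-up means. The largest saving is 1 − 0.81 = 19% of N.

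**4. Other settings.**
- Proportional relation (ratio SD 0.3 to 0.5): adding baseline changes power by 0.0 to −0.2 points in either model. A smaller run reached −0.4 (linear model) and −0.3 (rank model).
- Fifteen centres of 20, linear relation: gains of 0.0 to +8.7 (linear model) and 0.0 to +5.8 (rank model).
- Deaths of 20%, ranked worst, risk rising with baseline and no effect on death: the rank model changes by −0.2 to +2.1 points.

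**5. Error rates under no effect.** Baseline means differ by more than 0.6 points in 8–9% of trials. In those, the linear model without baseline rejects in 5.8–14.1% (linear relation) or 4.3–5.1% (proportional); with baseline it rejects in 3.9–6.0%. Over all trials, reporting whichever of the two mixed models is significant gives 5.4–7.1% (linear relation) or 5.0–5.6% (proportional). Taking any of four analyses (centre-stratified Wilcoxon, meta-analysis, mixed model with or without baseline) gives 8.2–10.6% (linear relation) or 6.7–7.2% (proportional).

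**6. Which model to make primary.** Where the relation is linear, the linear model of R with baseline had 1.2 to 5.8 points less power than a centre-stratified Wilcoxon test. Adding the covariate to a plain linear model of relative change is therefore not enough to make it the best primary analysis.

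**The case against.** The best defence has four parts.

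- **Randomisation makes the unadjusted comparison valid.** This stands. A reader might infer that the SOFA result would be biased; the documents do not support that. The raised rejection rates in step 5 are conditional on an imbalance that has already occurred, not overall error rates.
- **Baseline is already used, and the mixed model may include it.** Both are true. Baseline is the reference value of the endpoint, and the description of the mixed model is open-ended. A reader might infer that the plan ignores baseline SOFA or shuts it out of the model; it does neither. What remains is that nothing commits to it as a covariate.
- **The gain is small and rests on assumptions.** Largely right. Three of the six linear settings gain under 1 point in the linear model, and the proportional settings gain nothing. Raising the assumed baseline floor from 2 to 4 cuts the linear model's range to 0 to 5.3 points; a baseline mean of 10 leaves it similar (up to 9.6). The textbook variance ratio (1 + ρ)/2, which is 0.65 to 0.85 for ρ = 0.3 to 0.7, might suggest a 15–35% saving in N. It applies to absolute change with equal variances, not to this endpoint.
- **Two matters are joined.** Fair. The 8.2–10.6% for any of four analyses comes mainly from having no primary step. The covariate choice alone reaches only about 7%.

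**Conclusion.** The point holds as an optional improvement. It is not a fault that invalidates the comparison. The text commits baseline SOFA to no effect analysis beyond its role in the endpoint, and it ranks none of its three analysis steps. That reading needs no assumed numbers.

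The size does. Under the stated inputs, with follow-up linear in baseline, adding baseline SOFA is worth about 0 to 9 power points in a linear model and 0 to 7 in a rank-based one. It is worth about nothing at correlation 0.7 or under proportionality, and −0.2 to +2.1 points in the rank model if 20% die and are ranked worst. Confidence in the size is moderate: the correlation and the shape of the relation decide it, and the documents inform neither. The check takes one follow-up score per patient and does not model the choice among the listed days.

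**What to change.** Before outcome data by arm are examined:

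1. State the formula for relative change.
2. Name one primary SOFA analysis across centres: a rank-based model of relative change with arm, baseline SOFA and centre.
3. Label the centre-by-centre tests, the meta-analysis and any linear mixed model as supportive, and put baseline SOFA in that mixed model too.
4. To give an effect size, add as supportive an ANCOVA of follow-up SOFA on arm, baseline SOFA and centre, reporting the adjusted difference with its 95% CI.

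The deadline is set by access to outcome data because the documents describe no blinding.

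The cost is SAP wording and slightly more analysis. No new data are needed and relative change remains the endpoint. The loss of power from adding baseline SOFA was under 0.5 point in the settings tried. A proportional-odds model is an alternative, but its odds ratio changes the summary measure, and it was checked only on pooled patients without centre. Making the ANCOVA primary would also change the summary measure. In pooled runs without centres, it lost up to 4.3 points against a Wilcoxon test of relative change when the relation was strictly proportional.
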